9.4 Statistical Analyses

9.4.1 General Considerations

The statistical analysis plan (SAP) will be developed and finalized before database lock and will describe the subject populations to be included in the analyses, and procedures for accounting for missing, unused, and spurious data. This section is a summary of the planned statistical analyses of the primary and secondary endpoints.

All statistical testing will be 2-sided at significance level of 0.05 and no multiplicity adjustment will be made.

9.4.2 Primary Endpoint

The primary efficacy variable is:

• Duration of episode (DOE) will be measured in hours (using the Science 37 Platform), of a single treated HL lesion. Observation period to determine healing will last up to 14 days (DurEp14).

Duration of episode (DOE) is defined as the time from the initiation of treatment (study intervention) to the healing of primary lesions (loss of crust) for participants who experience a vesicular lesion. For participants whose primary lesions are not vesicular in nature, duration of episode is the time from study intervention initiation to the return to normal skin as determined by the independent blinded reader of the participant's face images using a 6-point Likert scale or the cessation of symptoms, whichever comes last. For the subjects who do not demonstrate the healing of primary lesions or cessation of symptoms, the data will be censored at 14 days (14*24 hours) or time of loss of follow-up, whichever happens earlier.

Duration of episode (DOE) will be estimated and plotted using Kaplan-Meier method and analyzed using log-rank test.

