This is a 14-day clinical trial (Treatment Phase) to test the hypothesis that Sitavig (acyclovir) buccal tablet safely and effectively reduces duration of a herpes labialis cold sore of the lip in immunocompetent adults. Eligible participants who pass screening procedures will be randomized and moved into the Run-in Phase. Participants will be randomly assigned one of two treatment groups - Sitavig (acyclovir) 50 mg buccal tablets or a placebo buccal tablet. The randomization assignment is such that there is a 1 in 2 chance of receiving the placebo treatment. Participants will have a 6 month eligibility window in which they can self-initiate treatment should prodromal symptoms start. At the start of prodromal symptoms, participants will self-

Version 5.0

Page: 17 of 68

initiate treatment and record face images as well as symptom scores over the next 14 days. Treatment consists of a single application (of the buccal tablet) beginning on Day 1. Face images and symptom scores are captured over the 14 day Treatment Phase.

Study Duration (Treatment Phase): 14 days

Study Duration (Follow up Phase): 12 months

Investigational Medicinal Product (IMP): Sitavig (acyclovir) 50 mg buccal tablet or placebo buccal tablet

Treatment Duration: 1 day

Visit Frequency: After the start of treatment, two visits within the 14 day Treatment Phase. Additional follow up by phone will occur at 3, 6, 9 and 12 months after treatment.

Condition/Disease: Herpes labialis of the lips caused by herpes simplex virus type 1 (HSV-1) or herpes simplex virus type 2 (HSV-2).

Study Hypothesis: Sitavig (acyclovir) buccal tablet effectively reduces the duration of a cold sore of the lips.

Health Measurement/Observation: Independent blinded lesion evaluation using a 6-point Likert scale and 0-10 NRS symptom scores will occur pre and post treatment.

Intervention Groups: Participants will be randomized in 1:1 fashion (active or placebo) with a single dose of study intervention.

Data Monitoring/Other Committee: No

Version 5.0 Page: 18 of 68

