^c Face images taken at 09:00, 14:00 and 19:00 each day.

^d The 2-day window pertains to all Visit 3 tasks except the NRS symptom scores, face images, QoL-OHIP and Global assessment which should be collected at their respective nominal times (±60 minutes) on Day 14.

^e Face image(s) and NRS symptom score(s) required if a new outbreak of herpes labialis is suspected by the investigator.

^f After successful completion of all screening procedures.

^g Follow up dates established using the Day 1 dosing date.

Version 5.0 Page: 20 of 68

2. Introduction

Herpes labialis (HL), also called cold sores of the lip, is an infection primarily caused by herpes simplex virus type 1 (HSV-1) and occasionally herpes simplex virus type 2 (HSV-2). The infection is typically spread between people by direct contact. HL is a rash of the skin and mucous membranes (in particular, the lips) and is characterized by erythema and blisters that are preceded and accompanied by tingling, itching or burning pain [1].

For an infection to manifest, the virus must come in contact with mucosal surfaces or abraded skin. The viral replication takes place at the site of primary infection (epithelial cells), either as an intact virion or the capsid is transported in a retrograde fashion by neurons to the dorsal root ganglia, where, after another round of viral replication, latency is established. After primary infection, the virus recedes via the sensory nerve into the respective ganglion (usually the trigeminal ganglion), where it lies latent throughout the individual's lifetime. Stimuli such as fever, menstruation, sunlight, and upper respiratory infections can reactivate the virus, after which it returns to the epithelial cells via the sensory nerve [2].

HSV1 and HSV2 infections rest in a dormant (inactive) state until the virus is activated. During an active phase of infection, a visible outbreak of sores may be observed. Infrequently, life-threatening infection (e.g., encephalitis) may occur. The more severe the primary infection (as reflected by the size, number, and extent of lesions) the more likely it may be that recurrences may develop when triggered [3,4].

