3.4 Study Day

The study day for each assessment/event of a subject will be derived using their first study drug administration date. For the assessments performed on or after first study drug administration date, study day is calculated as

Study Day = (Date of assessment/event – Date of first study drug administration) + 1

For the assessments performed prior to first study drug administration, study day is calculated as

Study Day = (Date of assessment/event – Date of first study drug administration)

The summary and analysis will be performed considering the different timepoint when the assessment was conducted.

CONFIDENTIAL Page 16 of 31

Private and Confidential Study No 21755 Date: DEC 18, 2023

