4 DEFINITIONS AND DERIVATIONS

Run-in Failures: Run-in failures are participants who successfully completed screening and randomized to a blinded study intervention (treatment). Participants start a 6-month eligibility window during the Run-in Phase where they could potentially self-initiate treatment. Participants who are considered a Run-in failure occur because of the following:

- Randomized participants with no prodromal symptoms after 6 months
- Met an exclusion criterion (e.g., medication, pregnancy)
- Adverse event or change in medical history that requires study withdrawal
- Withdraw of informed consent by the participant
- Study intervention kit not available
- Lack of compliance as determined by the Investigator/designee

Baseline: Baseline value is defined as the last non missing assessment prior to first administration of the study drug. If the assessment occurs on the same day as the first study drug administration, then the time of assessment should be compared to the time of first dose administration to derive the baseline value.

Post-baseline: The Post-baseline values are defined as assessments taken after the first administration of study drug/treatment.

Change from Baseline = $(post\ baseline\ value - baseline\ value)$.

Duration of Episode (DOE): DOE is defined as the time from the initiation of treatment to the healing of primary lesions (loss of crust) for subjects who experience a vesicular lesion. For subjects whose primary lesions are not vesicular in nature, DOE is the time from study intervention initiation to the return to normal skin as determined by the independent blinded reader of the subject's face images using a 6-point Likert scale or the cessation of symptoms, whichever comes last. For the subjects who do not demonstrate the healing of primary lesions or cessation of symptoms, the data will be censored at 14 days (14*24 hours) regardless of any circumstances. If time (hour) is missing for either treatment initiation or the healing of primary lesion or both, however, both dates are recorded, then DOE is number of days (end date – start date) *24. If only healing ending date and/or time are missing, DOE will be imputed as 14*24 hours. If date of treatment initiation is missing, then DOE will be missing.

CONFIDENTIAL Page 17 of 31

Private and Confidential Study No 21755 Date: DEC 18, 2023

DOE (hours) = (Date and time of healing of primary lesions – Date and time of first treatment administered)

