5.3 Other Endpoints

Following are the **other endpoints** of the study:

- ➤ Duration of episode (DOE) will be measured in hours (using the Science 37 Platform), of a single treated HL lesion in subjects who initiation study intervention within 1 hour of onset of prodromal symptoms and subjects who initiated study intervention more than 1 hour after onset of prodromal symptoms.
- Time to cessation of symptoms, measured in hours from initial application of assigned study intervention. Cessation of symptoms is defined as the absence of sensations of pain, tenderness tingling, itching or discomfort at the site of the cold sore as measured by NRS.
- ➤ Quality of life score, as measured by the OHIP-14 questionnaire at 3-, 7- and 14-days post-dose.
- ➤ Global assessment of study intervention at Day 14.
- > The change from baseline to post-dose in NRS.
- The incidence of detachment or swallowing within 6 hours of dosing and the number (percentage) of subjects with the incidence.
- ➤ The percentage of subjects who replace the tablet among those with detachment or swallowing within 6 hours of dosing.

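### The 336-hour censoring and imputation time lies 4 to 30 hours beyond the last scheduled assessment, and the days-post-dose labels overstate when quality of life and the global evaluation are measured (minor)

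*Protocol*

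**What the plan says.** **The clock and its limit.** Protocol 9.4.2 starts the clock at dosing: "Duration of episode (DOE) is defined as the time from the initiation of treatment (study intervention) to the healing of primary lesions". For participants who have not healed, "the data will be censored at 14 days (14*24 hours) or time of loss of follow-up, whichever happens earlier". SAP section 4 sets the same limit without the loss-to-follow-up clause: "the data will be censored at 14 days (14*24 hours) regardless of any circumstances". It applies that limit to time to cessation of symptoms as well. For a missing healing time, SAP section 4 says "If only healing ending date and/or time are missing, DOE will be imputed as 14*24 hours", and SAP 3.3 has a matching rule for healed lesions.

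**The day count.** Protocol 1.1 says "Treatment consists of a single application (of the buccal tablet) beginning on Day 1". The Study Day formula in SAP 3.4 ends "Date of first study drug administration) + 1", so there is no Day 0.

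**The schedule.** Images and symptom scores are taken at 09:00, 14:00 and 19:00, with Day 14 as the last day (Protocol 1.3 and 8.1.5). Visit 3 has a +2-day window. Footnote d of Protocol 1.3 and section 8.1.5.6 exclude the symptom scores, images, OHIP-14 and Global assessment from it, "which should be collected at their respective nominal times (±60 minutes) on Day 14".

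**The labels.** SAP 5.3 describes quality of life "as measured by the OHIP-14 questionnaire at 3-, 7- and 14-days post-dose". Protocol 8.1.5 schedules OHIP-14 at 09:00 on Days 3, 7 and 14. The Global evaluation is called 14 days post-dose in Protocol 8.2.3 and SAP 9.3, and is scheduled at 19:00 on Day 14.

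**The concern.** The limit is written in hours, for an endpoint measured in hours from dosing, so it has to be a time the schedule can reach. If it is not, three things follow.

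- Unhealed completers are credited with follow-up they did not have. They stay in the risk set after their own last image while participants dosed earlier in the day can still have events.
- A healed lesion with a missing end time receives a value later than any healing the schedule could record.
- Quality-of-life and Global results carry a time label later than the time of measurement. This matters most for the first OHIP-14 score, in an illness that Protocol section 2 says lasts around 7 to 10 days.

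**Working it through.** **Stated figure.** 14 × 24 = 336 h from dosing. The multiplication is correct. The question is whether any scheduled assessment reaches 336 h.

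**Inputs.** Dosing on Day 1 at clock hour t, from 0 to just under 24. Study Day d is d − 1 dates after dosing (SAP 3.4). Assessment at clock hour c (Protocol 8.1.5), ±1 h. Protocol 8.1.4 allows dosing after 19:00. Assessments then start the next morning, and the day count does not shift.

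**Formula.** Elapsed hours = (d − 1) × 24 + c − t.

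**Last image and symptom score** (d = 14, c = 19): 13 × 24 + 19 − t = 331 − t.

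| Dosing time | Last assessment (h) | Short of 336 h by (h) |
|---|---|---|
| 00:00 | 331 | 5 |
| 08:00 | 323 | 13 |
| 12:00 | 319 | 17 |
| 19:00 | 312 | 24 |
| 20:00 | 311 | 25 |
| 23:59 | 307 | 29 |

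The nominal range is 307–331 h. With ±60 minutes it is 306–332 h (12.75 to 13.83 days), a shortfall of 4 to 30 h. No dosing time reaches 336 h.

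**Labelled assessments**, including ±60 minutes:

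| Assessment | Formula | Actual (h) | Label (h) | Early by (h) |
|---|---|---|---|---|
| OHIP-14, Day 3, 09:00 | 57 − t | 32–58 | 72 | 14–40 |
| OHIP-14, Day 7, 09:00 | 153 − t | 128–154 | 168 | 14–40 |
| OHIP-14, Day 14, 09:00 | 321 − t | 296–322 | 336 | 14–40 |
| Global, Day 14, 19:00 | 331 − t | 306–332 | 336 | 4–30 |

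**Cross-check within the SAP.** When a clock time is missing, section 4 computes duration as the date difference times 24. Healing on Day 14 then gives 13 × 24 = 312 h. The SAP thus assigns 312 h to healing on the final day and 336 h to not having healed by the end of that day.

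**Effect on the primary test.** For completers, censoring at the last assessment instead of 336 h can change a risk set only at event times after someone's last assessment, so only after about 306 h. Before that, both rules give identical curves. Episodes of 7 to 10 days are 168–240 h, so the medians should not move.

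An illustrative simulation used assumptions that are not in the documents: 200 per arm, Weibull healing times with shape 2 and scales of 8 and 9 days, dosing uniform from 07:00 to 23:00, and 200 replicates. About 9% of participants were censored. Switching between the two rules moved the log-rank Z by 0.04 on average and by 0.15 at most. The share of significant results was 0.61 under one rule and 0.60 under the other.

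**The case against.** The best defence is that the endpoint's observation period is described as lasting up to 14 days, which is a ceiling. The schedule covers 14 calendar days counting Day 1, and the per-protocol requirement of 14 days of evaluations can be read the same way. This defence stands. A reader might infer that the trial fails to deliver its observation period, and the documents do not support that. The conflict is confined to the explicit 14*24 hours and to the days-post-dose wording.

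A reader might also infer that late healers are misclassified as treatment failures at 14 days. The documents do not support that either. No planned endpoint is a proportion healed at 336 h. Duration is analysed by Kaplan-Meier, log-rank and Cox methods, in which an unhealed completer is censored. The documents also give no rate from which a misclassified share could be calculated.

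The schedule is the same in both arms, so the offset does not favour either. For OHIP-14, the operational sections fix the assessment day and hour, and SAP 7.7.3 summarises by scheduled visit, so that part is a matter of labelling.

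What remains is an hour limit that the schedule cannot reach, used for both censoring and imputation, and time labels that do not match the assessments.

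**Conclusion.** The inconsistency is real and minor. The 336 h limit is 4 to 30 h later than the last scheduled image or symptom score for every participant. OHIP-14 is taken 14 to 40 h before its labelled times, and the Global evaluation 4 to 30 h before its own. These ranges use only the documents' day numbering, clock times and ±60-minute window, with dosing possible at any hour.

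The consequence is limited to the Kaplan-Meier tail after about 306 h (survival probabilities are a planned output in SAP 7.7.1), the 336 h imputed values and the reported assessment times. The effect on medians and the log-rank test is negligible. That follows from the risk-set argument, and the simulation illustrates it under its own assumptions.

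The SAP's rule of censoring early dropouts at 336 h, where the protocol censors at loss to follow-up, is a separate and larger matter. It should not add weight to this point.

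**What to change.** Make these wording changes:

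1. In Protocol 9.4.2 and SAP section 4, censor unhealed completers at the actual time of their last face image or symptom score, replacing 14*24 hours. Apply the same rule to time to cessation of symptoms in SAP section 4.
2. Describe DurEp14 as observation through the Day 14 19:00 assessment.
3. In SAP 3.3 and section 4, bring the 336 h imputation for missing healing times into line with the last observable time. Do this together with item 1. If healed participants kept an imputed event at 336 h while all unhealed completers were censored by 332 h, only imputed cases could remain at risk among completers, and the curve would drop sharply at its end.
4. Label OHIP-14 results as Study Days 3, 7 and 14, and the Global evaluation as Study Day 14.

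The cost is text and minor programming, with no new data. The downside is that the stated window becomes about 13 elapsed days.

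Keeping 336 h by adding captures on Day 15 is not a clean alternative. A 19:00 capture that day falls at 355 − t hours, which nominally misses 336 h for any dose after 19:00, and footnote d would have to be rewritten to allow it.

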9.4.3 Secondary Endpoints

- Incidence of aborted lesions, defined as treated HL lesions that do not progress to the vesicular or crust stage. A lesion that returns to normal skin without forming a vesicle or crust will be counted as an aborted lesion. Observation period to determine healing will last up to 14 days (Abort14). The incidence of aborted lesions will be analyzed using Chi-square test.
- Incidence of recurrence of HL lesions during the 12-month follow-up period (IncRec12) will be analyzed using Chi-square test.
- Time to recurrence of HL lesions, measured in days from resolution of the cold sore treated in the Treatment phase until appearance of a cold sore during the follow-up period (TimeRec12). The time to recurrence is determined by assessment from the investigator and documented using NRS symptom scores and face images using the Science 37 Platform. For subjects who do not recur during the follow-up period, the data will be censored at the time of last follow-up. Time to recurrence of HL lesions will be analyzed similarly to the primary endpoint.

Version 5.0 Page: 50 of 68

• Safety and tolerability measured by the Incidence of Treatment-Emergent Adverse Events

• The percentage of participants who have at least one recurrence during the 12-month follow up period will be analyzed using Chi-square test.

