8.1.4 Treatment/Evaluation Phase (Day 1)

Participants who start to experience prodromal symptoms before the visible appearance of any signs of HL must document the start time of symptoms in Science 37 Platform, complete a pre-dose (immediately before dosing) 0-10 NRS cold sore symptom evaluation (pain, burning sensation, itching and swelling) and a face image. Prior to the start of study intervention, all WOCBP participants MUST perform a urine pregnancy test, and verify that the results are negative (not pregnant), and record in the Science 37 Platform. After verification of a negative pregnancy test result, the participant may self-initiate study intervention.

Any participant who has a positive pregnancy test or is not sure of the results must contact the Science 37 study team immediately. Participants with a verified positive pregnancy test must not self-administer study intervention and will be withdrawn from the study.

Participants must always record pre-dose NRS and a face image irrespective of the start time of prodromal symptoms in the Science 37 Platform. After the completion of all pre-dose procedures, participants will be instructed to self-administer one (1) tablet. Should the buccal tablet adhere to the upper gum correctly, a second dose/tablet is NOT applied. A second tablet in the treatment kit is provided and labeled "BACKUP". The backup tablet should only be used if an issue occurs applying the first tablet (see Section 6.5).

After dosing, participants will complete the 0-10 NRS cold sore symptom evaluation, and face images at 09:00, 14:00 and 19:00 that day within Science 37 Platform. Depending on time of day study intervention is started, some Day 1 assessments and face images may not be collected if the time (minus the 60 minute window) occurs before the time of dosing. If dosing is started after 19:00, then post-dose NRS and face images will be collected starting the next day at 09:00. All post-dose time point assessments (NRS and face images) have an allowable window of ± 60 minutes.

Version 5.0

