8.2.4 Face Image Interpretation

Participants face images pre and post-study intervention will be evaluated by an independent reader blinded to the study intervention administered. Lesion interpretation will be done using a 6-point Likert scale.

- 0 = Normal lip
- 1 = Erythema
- 2 = Papule
- 3 = Vesicle
- 4 = Ulcer
- 5 = Crust

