2.4 Randomization

Subjects will be randomized in a 1:1 ratio to either of the treatment groups (Sitavig or placebo). At Screening, qualified subjects will be assigned a unique number (Randomization Number, [RNR]) in ascending numerical order according to the randomization schedule generated prior to the study by Statistics Department at Bayer.

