End of Treatment Phase: The end of the Treatment Phase for a subject is defined as the date (time) of the last visit in the Treatment Phase.

End of Study: The end of the study is defined as the date of the last follow-up visit (either by documented HL outbreak or at 12 months) of the subject in the study. A subject is considered to have completed the study if he/she has completed all phases of the study up to Follow up Phase.

Aborted Lesion: It is defined as a treated HL lesions that do not progress to the vesicular or crust stage. A lesion that returns to normal skin without forming a vesicle or crust will be counted as an aborted lesion i.e., for this lesion the face image interpretation Likert score will be less than or equal 2 and will never reach a score of 3 or above before healing.

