7.7.2 Analysis of Secondary Efficacy Endpoints

- ➤ Incidence of aborted lesions, defined as treated HL lesions that do not progress to the vesicular or crust stage. A lesion that returns to normal skin without forming a vesicle or crust will be counted as an aborted lesion. Observation period to determine healing will last up to 14 days. The incidence(events) of aborted lesions will be reported by treatment groups and proportions of subjects with at least one Incidence of Aborted Lesions will be compared between the two treatment groups using the Chi square or Fisher's Exact test for categorical data for both ITT and PP populations. Individual subject data for aborted lesions will be presented in Listing.
- ➤ Incidence of recurrence of HL lesions during the 12-month follow-up period will be reported by treatment groups for FU population. Recurrence is determined by assessment from the investigator and documented using NRS symptom scores and face images using the Science 37 Platform.

The percentage of subjects with at least one recurrence of HL lesions during the 12-month follow-up period will be compared between the two treatment groups using the Chi square or Fisher's Exact test for homogeneity of proportions for categorical data using FU population.

CONFIDENTIAL Page 23 of 31

Private and Confidential Study No 21755 Date: DEC 18, 2023

Individual subject data for recurrence of HL lesions will be presented in Listing.

> Time to recurrence of HL lesions, measured in days from resolution of the cold sore treated in the Treatment phase until appearance of a cold sore during the follow-up period. For subjects who do not recur during the follow-up period, the data will be censored at the time of last follow-up. Time to recurrence of HL lesions will be analyzed similarly to the analysis of primary endpoint using KM method for FU population. Individual subject data Listing for time to recurrence of HL lesions will be presented.

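### Aborted lesions get a valid but unadjusted test and no prespecified between-arm difference with a confidence interval, although two pre-treatment predictors are already collected

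*Protocol*

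**What the plan says.** **Test.** Protocol 9.4.3: "The incidence of aborted lesions will be analyzed using Chi-square test". SAP 7.7.2 reports incidence by arm, with the proportions "compared between the two treatment groups using the Chi square or Fisher's Exact test for categorical data for both ITT and PP populations". Neither section names a covariate or stratum, or asks for a risk difference, risk ratio or odds ratio with a confidence interval. For duration of episode, by contrast, SAP 7.7.1 pairs the log-rank test with a hazard ratio and 95% CI.

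**Error rate.** Protocol 9.4.1: "All statistical testing will be 2-sided at significance level of 0.05 and no multiplicity adjustment will be made".

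**Definition.** SAP section 4 requires that an aborted lesion "will never reach a score of 3 or above before healing".

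**Pre-treatment data.** Protocol 8.1.4: "Participants must always record pre-dose NRS and a face image irrespective of the start time of prodromal symptoms". The same section has the symptom start time documented, and Protocol 6.5 has the dosing time recorded. Protocol 8.2.4: "Participants face images pre and post-study intervention will be evaluated by an independent reader", who is blinded to treatment and uses a 0 to 5 scale. The 1-hour dosing split is applied only to duration of episode (Protocol 9.4.4, SAP 7.7.3).

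**Not available.** The sample size is redacted. No abort rates or pre-dose score distribution are given. Protocol 2.2 says only that more treated patients had aborted lesions in the earlier trial.

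**The concern.** Whether a lesion aborts plausibly depends on how far it had gone when the tablet was applied. A normal lip shortly after the first tingle is a different starting point from a papule some hours later, and a vesicle has already failed the definition. Dosing within one hour and before visible signs is a stated preference (Protocol 4.1.1.3), so a spread of starting points is possible.

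An unadjusted comparison leaves that spread in the noise. Pre-dose score and delay arise after randomisation but before the blinded tablet is applied, so treatment cannot affect them and stratifying on them introduces no bias. At stake are some power on this endpoint and a prespecified statement of how large the effect is and how precisely it is known.

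**Working it through.** No figure in the plan can be reproduced, because sample size, power and abort rates are redacted or absent. From the documents: two-sided 0.05, 1:1 allocation, the tests and the definition. Every rate, score mix, odds ratio (OR) and sample size below is an assumption.

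**1. What the definition alone implies.** Let a share f of lesions be at score 3 or above at dosing. They have no events in either arm. Take 30% v 40% aborting among the rest and 356 per arm, which gives 80% power when f = 0. With n per arm,

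power = Φ{ [|p1 − p0|√n − 1.96√(2p̄(1 − p̄))] / √[p0(1 − p0) + p1(1 − p1)] }.

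For f = 10%, one pooled table has 27% v 36%: (0.09×√356 − 1.96×√(2×0.315×0.685)) / √(0.1971 + 0.2304) = (1.698 − 1.288)/0.654 = 0.628, so power is 73.5%. In a stratum of their own, these lesions add nothing to the Cochran-Mantel-Haenszel (CMH) statistic. That leaves 356×0.9 = 320.4 per arm at 30% v 40%: (1.790 − 1.322)/0.671 = 0.697, so 75.7%.

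| Share at score 3+ | Pooled | Separated | Gain (points) |
|---|---|---|---|
| 0% | 80.0% | 80.0% | 0 |
| 10% | 73.5% | 75.7% | 2.2 |
| 20% | 66.2% | 70.7% | 4.5 |
| 30% | 58.4% | 64.9% | 6.5 |

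Stratifying recovers only part of the loss.

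**2. Spread across scores 0, 1 and 2.** Assume a 50/30/20% mix and a common OR. R² is the between-score variance of the placebo abort probability divided by p(1 − p). For rates 55/25/8%, p = 0.275 + 0.075 + 0.016 = 0.366, the between-score variance is 0.5×0.184² + 0.3×0.116² + 0.2×0.286² = 0.0373, and R² = 0.0373/0.232 = 16%. The other two rate sets give 6% and 26%. Simulated power (20,000 trials each), pooled z-test v Mantel-Haenszel by score:

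| Placebo rates | Per arm | OR | Unadjusted | Stratified | Gain (points) |
|---|---|---|---|---|---|
| 45/30/15% | 300 | 1.5 | 61.4% | 64.6% | 3.2 |
| 55/25/8% | 150 | 1.5 | 30.3% | 34.6% | 4.3 |
| 55/25/8% | 150 | 1.8 | 55.4% | 62.0% | 6.6 |
| 55/25/8% | 300 | 1.5 | 52.1% | 59.9% | 7.8 |
| 62/20/4% | 150 | 1.8 | 44.1% | 55.5% | 11.4 |
| 62/20/4% | 300 | 1.5 | 42.4% | 54.1% | 11.7 |

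A 6,000-trial run of the last row gave 42% to 55%, or 13 points. With no prognostic effect (150 per arm, OR 1.5), power was 39.4% v 39.2%.

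**3. Most participants dosing at score 0.** Same rates, 150 and 300 per arm, OR 1.5 and 1.8; gain in points:

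| Mix 0/1/2 | 45/30/15% | 55/25/8% | 62/20/4% |
|---|---|---|---|
| 80/15/5% | about −1 to +0.6 | 0.4 to 2.8 | 2.5 to 6 |
| 90/7/3% | −1.6 to 0 | 0 to 1.2 | about 3 to 4 |

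Across repeated runs with 80-90% at score 0, the change lay between about −2 and +7 points.

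**4. Adding delay.** Logistic regression on score and dosing after 1 hour (40% late, 50/30/20% mix, 30% v 40% overall, 3,000 trials), chi-square v adjusted:

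- Not prognostic: 82.3% v 81.5% at 356 per arm.
- Weak (OR 0.67 per score step, 0.74 for late dosing): 81.7% v 82.9% at 356.
- Moderate (0.45, 0.55): 45.4% v 49.4% at 150; 72.2% v 76.8% at 300.
- Strong (0.22, 0.37): 43.3% v 52.2% at 150; 72.1% v 81.6% at 300.

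An eight-stratum CMH test (four score groups by two delay groups) gained about 3 to 6 points at 150 to 300 per arm under assumed rates.

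**5. Validity.** Under the null, chi-square and logistic tests rejected in 4.4% to 5.1% of trials at 300 per arm. The pooled z-test and Mantel-Haenszel by score rejected in 4.8% to 5.4%, and the eight-stratum test in about 5%.

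**6. The interval not asked for.** At 30% v 40%, the half-width is 1.96×√[(0.21 + 0.24)/n]: 7.0 points at 356 per arm and 10.7 at 150.

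**The case against.** The strongest reply is that nothing here is invalid. Allocation is 1:1, no stratification factors are described, and the unadjusted test holds its error rate. That stands.

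A reader might infer that the endpoint simply loses power as planned. The documents do not support that as a flat statement: they give no abort rates, no score mix and no association with delay. The 50/30/20% mix puts half of the participants at a visible stage at dosing, whereas the protocol asks for dosing at prodrome and preferably before visible signs. If they do as asked, the gain is mostly small and can be slightly negative. This also stands, and the larger gains need both a late mix and a steep gradient.

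A reader might also infer that the plan yields nothing but a p-value. That goes too far. SAP 7.7.2 reports incidence by arm and SAP 3.1 calls for numbers and percentages, so the crude difference can be read off. What is missing is its confidence interval.

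Finally, five score groups (including missing) by two delay groups make up to ten cells. The 3-or-above cells add nothing to the test. In PP, the primary population, the late-dosing cells could be thin: late dosing is recorded as a deviation, and the documents do not say whether it is a major one. This is a fair practical point, and it calls for a merging rule.

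**Conclusion.** The point holds as one of efficiency and reporting. The planned test is valid and unadjusted, and no between-arm difference with a confidence interval is prespecified. That much is certain from the text. It is also certain that a lesion at score 3 or above at dosing cannot count as aborted, so pre-dose score is prognostic to that extent.

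The size of any power gain is not certain. Under the assumptions shown, it runs from about zero, or a point or two lost, when nearly all dose at score 0, to about 10-13 points when the mix and the gradient are both strong. Neither end can be called the expected value. The missing interval is worth correcting even if the power gain proves negligible.

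**What to change.** In SAP 7.7.2, with Protocol 9.4.3 brought into line or the change listed in SAP 7.13:

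- Analyse aborted lesions by a CMH test stratified by pre-dose image score (0; 1; 2; 3 or above; missing) and dosing within or after 1 hour of prodrome onset. Say where a participant without a recorded onset time is placed.
- Fix a merging rule for sparse strata before unblinding: for example, drop the delay split first, then combine scores 1 and 2.
- Report the Mantel-Haenszel risk difference with 95% CI in PP and ITT. The 3-or-above stratum enters it with a difference of zero but keeps its weight, so the estimate still describes everyone analysed.
- Keep the unadjusted chi-square or Fisher test as supportive.

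The cost is SAP wording, one procedure option and the merging rule. No new data are needed. The downside is a small possible loss of power if the predictors turn out not to be prognostic.
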